11.3 Criteria for Causal Relationship to the (Study) Drug

Not applicable. This survey does not involve patient-specific data collection, does not involve exposure to a study drug, and does not include questions that could potential identify an AE report.

Nevertheless, should an HCP report an AE to study personnel associated with the use of ENJAYMO™, study personnel should assume there is a reasonable possibility that the event may have been caused by ENJAYMO™.

11.4 Procedure in Case of Pregnancy

This direct-to-HCP survey does not involve patient-specific data collection and does not involve exposure to a study drug. In this survey, HCPs are the research subjects and will complete an online survey via a secure website. The online survey does not include questions that could potentially identify a pregnancy.

Nevertheless, should a HCP report a female patient, or partner of a male patient, becoming pregnant who was exposed to ENJAYMO™, study personnel must report the pregnancy as if it is an AE according to the timelines specified in [Section 11.5](#).

11.5 Notification of Adverse Drug Reactions (Serious and Non-serious) by Study Personnel to Sponsor

This survey does not involve patient-specific data collection and does not include questions that could potential identify an AE. HCPs who participate in the survey are not study

investigators; they are research subjects. Therefore, HCPs are not requested nor expected to report AEs.

Nevertheless, should a HCP report an AE to study personnel, study personnel must report SAEs immediately (within 24 hours of awareness), while non-serious AEs should be reported within 30 days of awareness.

For reporting to Global Pharmacovigilance –

Fax: [REDACTED]

Email: [REDACTED]

12 PLANS FOR DISSEMINATING AND COMMUNICATING STUDY RESULTS

The results of this study will be summarised in a study report that, after review and approval by Sanofi, will be communicated to the applicable health authorities within the agreed timeframe. Protocol details and an abstract of results will be posted as per guidelines for studies meeting the criteria for PASS. A scientific publication may be considered. Authorship of any publications resulting from this study will be determined based on the International Committee of Medical Journal Editors Recommendations for the Conduct, Reporting, Editing, and Publication of Scholarly Work in Medical Journals.

14 ANNEXES

Annex 1: List of stand-alone documents

Number	Document reference number	Date	Title*
1	N/A	N/A	ENJAYMO™ Physician's Guide

Annex 3: Survey questionnaire

Please enter your Unique ID to participate in the survey. Your Unique ID was provided in your survey invitation.

Unique ID: **→ IF ENTERED, PROCEED TO COUNTRY AND LANGUAGE SELECTION, OTHERWISE, TERMINATE SURVEY**

The above section will only appear for respondents who did not receive their invitation directly by email from the Conformat survey software.

Surveys invitations will include a unique ID for each HCP which will need to be entered to access the survey.

Include a % Completed Bar at the top of the survey for respondents.

Correct responses are ticked as ✓ and will be removed for the actual survey.

Please select your country and language from the list below:

- Austria (German) → **PROCEED TO SURVEY INTRODUCTION**
- Germany (German) → **PROCEED TO SURVEY INTRODUCTION**
- Italy (Italian) → **PROCEED TO SURVEY INTRODUCTION**
- The Netherlands (Dutch) → **PROCEED TO SURVEY INTRODUCTION**
- My country is not listed → **THANK AND TERMINATE**

[Termination Language for Non-Qualified Candidates:]

Thank you for your interest in participating in this survey. However, we are required to limit participation to healthcare professionals who are from 1 of the 4 listed countries. We look forward to your potential participation in a future survey.

Survey Introduction

On behalf of Genzyme Europe BV (Sanofi), ICON is conducting a survey among healthcare professionals who prescribe ENJAYMO™ (sutimlimab). **Sanofi is required to perform this survey as mandated by the European Medicines Agency (EMA) in line with the ENJAYMO™ (sutimlimab) Risk Management Plan for Europe.** The overall goal of this study is to evaluate the effectiveness of the “**ENJAYMO™ Physician’s Guide.**” Participation in this survey is voluntary and will not affect your ability to prescribe ENJAYMO™.

The survey is expected to take up to 20 minutes to complete and is recommended to be completed in one sitting.

To complete the survey, you must meet study eligibility criteria. Please be assured that your individual answers will be held confidential. This study will summarise aggregated results provided by all participating healthcare professionals in order to protect the confidentiality of your individual answers.

By participating, you agree that ICON may contact you only in reference to this survey. You may withdraw from the survey at any time, in which case the information you have already provided will not be used in the final study report.

Please click on the NEXT button to verify that you qualify for this survey and to complete the required documentation for participation.

[BEGIN SURVEY SCREENING QUESTIONS]

S1. Does your practice include patients with cold agglutinin disease?

- Yes → **PROCEED TO S2**
- No → **PROVIDE A POP-UP THAT STATES** “Based on your answer, you are not eligible to take this survey. Please click “Next” to confirm your answer is correct, or click “Back” to review your answer”. **IF THE USER CLICKS ON ‘BACK’ THEN THE QUESTION WILL BE DISPLAYED AND THE RESPONSE CAN BE**

CHANGED. IF THE USER CLICKS ON ‘NEXT’ THEN THANK AND TERMINATE.

- S2. Do you provide your permission to share your anonymized survey responses, aggregated with all other survey responses, with the European Medicines Agency or national competent authorities?
- Yes → **PROCEED TO S3**
 - No → **PROVIDE A POP-UP THAT STATES** “Based on your answer, you are not eligible to take this survey. Please click “Next” to confirm your answer is correct, or click “Back” to review your answer”. **IF THE USER CLICKS ON ‘BACK’ THEN THE QUESTION WILL BE DISPLAYED AND THE RESPONSE CAN BE CHANGED. IF THE USER CLICKS ON ‘NEXT’ THEN THANK AND TERMINATE.**
- S3. Are you or have you been a direct employee of Sanofi, ICON, the European Medicines Agency, or other European-based National Competent Authorities within the past 5 years?
- Yes → **PROVIDE A POP-UP THAT STATES** “Based on your answer, you are not eligible to take this survey. Please click “Next” to confirm your answer is correct, or click “Back” to review your answer”. **IF THE USER CLICKS ON ‘BACK’ THEN THE QUESTION WILL BE DISPLAYED AND THE RESPONSE CAN BE CHANGED. IF THE USER CLICKS ON ‘NEXT’ THEN THANK AND TERMINATE.**
 - No → **PROCEED TO MAIN SURVEY**

[Termination Language for Non-Qualified Candidates:]

Thank you for your interest in participating in this survey. However, we are required to limit participation to healthcare professionals who meet the survey eligibility requirements. We look forward to your potential participation in a future survey.

[Language for Qualified Candidates:]

Thank you for your responses. You qualify for this survey, and we look forward to your participation. Once you enter the main survey, you will only be able to move forward through the questions.

[END SURVEY SCREENING QUESTIONS]

MAIN SURVEY

[Preamble 1]: These questions are about the risks of serious infections and meningococcal infections associated with ENJAYMO™ (sutimlimab). Please be sure to review all response choices for each question before answering each question. Please note that you will only be able to move forward in the survey as you complete each question.

CORRECT RESPONSES ARE CHECKED ✓

1. Did you receive the “ENJAYMO™ Physician’s Guide” that provides information to minimise the risks of serious infections and meningococcal infections associated with product use?
 - Yes
 - No
 - I don’t know/am not sure

2. Did you read the “ENJAYMO™ Physician’s Guide” that provides information to minimise the risks of serious infections and meningococcal infections associated with product use?
 - Yes
 - No
 - I don’t know/am not sure

3. ENJAYMO™ (sutimlimab) is indicated in adult patients with cold agglutinin disease (CAD) for the treatment of (Check all that apply) **RANDOMIZE ORDER OF THE FIRST 5 RESPONSES**
 - Hemolytic anaemia
 - Jaundice
 - Cardiac arrhythmia
 - Nausea and vomiting
 - Cold agglutinin syndrome
 - I don’t know/am not sure

4. ENJAYMO™ (sutimlimab) should only be prescribed to patients who have received appropriate vaccinations, especially against encapsulated bacteria.
 - True
 - False
 - I don’t know/am not sure

5. Are you familiar with current local guidelines or recommendations in patients with persistent complement deficiencies for meningococcal conjugate vaccine(s), meningococcal serogroup B vaccine(s), and pneumococcal vaccine(s)?

Yes
 No
 I don't know/am not sure

6. According to the ENJAYMO™ (sutimlimab) **Summary of Product Characteristics** and the “**ENJAYMO™ Physician’s Guide**”, which of the following warrant specific caution when using ENJAYMO™ (sutimlimab)? Please select all that apply.

Neisseria meningitides infection
 Hemophilus influenza infection
 Streptococcus pneumoniae infection
 Urinary tract infection
 All of the above
 I don't know/am not sure

7. According to the “**ENJAYMO™ Physician’s Guide**”, which of the following are important activities that are necessary when using ENJAYMO™ (sutimlimab):

		Yes, needs to be monitored	No, does not need to be monitored	I don't know/am not sure
A	Monitor patients for kidney damage			
B	Monitor patients for signs and symptoms of serious infections			
C	Take caution when prescribing ENJAYMO™ to patients who have chronic infections such as Hepatitis B, Hepatitis C or HIV			
D	Counsel patients about the risks of serious infection including meningitis			
E	Monitor patients for thyroid function			
F	Counsel patients about the risks of abnormal heart function			

8. According to recommendations in the “**ENJAYMO™ Physician’s Guide**,” you should counsel patients to seek immediate medical attention if they experience symptoms associated with risks of serious infections or meningococcal infections associated with ENJAYMO™ (sutimlimab). Please answer “True”, “False” or “I don't know/am not sure” to the following symptoms:

		True	False	I don't know/am not sure
A	Headache with stiff neck or back or confusion			
B	Fever, chills and rash			
C	Loss of appetite			
D	Muscle aches with flu-like symptoms			
E	Swelling in legs, ankles and feet			
F	Polyuria, dry mouth and blurred vision			

9. What is (are) the **primary source(s)** you use to learn about the appropriate indication, precautions for use, and potential risks for ENJAYMO™ (sutimlimab)? Please select all that apply. There are no correct/incorrect answers: **SELECT ALL THAT APPLY ANSWER – NO CORRECT RESPONSE.**

- Summary of Product Characteristics
- ENJAYMO™ Physician's Guide
- Professional Society or Congress
- The European Medicines Agency website
- Via specific discussions with Sanofi MSL
- Clinical practice guidelines; specify: _____
- Other (not listed above); specify: _____

[ON-LINE SURVEY - PROGRAMMER: RANDOMISE THE ORDER OF THE FIRST 5 RESPONSE OPTIONS]

HCP CHARACTERISTICS

[Preamble 2]: Below are 7 additional questions to help us combine your answers with other answers we have received, and to help us interpret the survey results. **THERE ARE NO CORRECT RESPONSES TO QUESTIONS 10, 11, 19, and 20. DISPLAY QUESTIONS 12-18 ON THE SAME PAGE.**

10. Approximately how many years have you been practicing as a physician?
- <5 years
 - 5 to <10 years
 - 10 to <15 years
 - ≥15 years
 - Prefer not to answer
11. Approximately how many patients have you treated with ENJAYMO™ (sutimlimab)?
- None → **PROCEED TO QUESTION 20**
 - < 5 patients → **PROCEED TO QUESTION 12**
 - 5-10 patients → **PROCEED TO QUESTION 12**
 - >10 patients → **PROCEED TO QUESTION 12**
 - Prefer not to answer → **PROCEED TO QUESTION 20**
12. For the most recent patient you prescribed ENJAYMO™ (sutimlimab), did you provide the patient with a copy of the ENJAYMO™ Patient Guide?
- Yes → **PROCEED TO QUESTION 13**
 - No → **PROCEED TO QUESTION 13**
 - I don't know/am not sure → **PROCEED TO QUESTION 13**
13. For the most recent patient you prescribed ENJAYMO™ (sutimlimab), did you confirm that their vaccination status is up-to-date according to local guidelines or recommendations for patients with persistent complement deficiencies?
- Yes → **PROCEED TO QUESTION 14**
 - No → **PROCEED TO QUESTION 19**
 - I don't know/am not sure → **PROCEED TO QUESTION 19**

14. For the most recent patient you prescribed ENJAYMO™ (sutimlimab), which vaccines did you check the status of? Please select all that apply.
- Meningococcal conjugate vaccine(s)
 - Meningococcal serogroup B vaccine(s)
 - Pneumococcal vaccine(s)
 - Other (not listed above); specify: _____
 - I don't know/am not sure
15. For the most recent patient you prescribed ENJAYMO™ (sutimlimab), was the patient up-to-date on their vaccinations?
- Yes → **PROCEED TO QUESTION 19**
 - No → **PROCEED TO QUESTION 16**
 - I don't know/am not sure → **PROCEED TO QUESTION 19**
16. For the most recent patient you prescribed ENJAYMO™ (sutimlimab), did you administer or prescribe vaccines to the patient?
- Yes → **PROCEED TO QUESTION 18**
 - No → **PROCEED TO QUESTION 17**
 - I don't know/am not sure → **PROCEED TO QUESTION 19**
17. For the most recent patient you prescribed ENJAYMO™ (sutimlimab), what was the reason you did not provide vaccination?
- The patient refused vaccination → **PROCEED TO QUESTION 19**
 - The patient received vaccination elsewhere → **PROCEED TO QUESTION 18**
 - I don't know/am not sure → **PROCEED TO QUESTION 19**
18. For the most recent patient you prescribed ENJAYMO™ (sutimlimab), when were vaccinations administered relative to starting of ENJAYMO™ (sutimlimab)?
- At the same time ENJAYMO™ treatment was started
 - Less than two weeks before ENJAYMO™ treatment was started
 - Two weeks before ENJAYMO™ treatment was started
 - I don't know/am not sure

19. For the most recent patient you prescribed ENJAYMO™ (sutimlimab), did you counsel them to seek immediate medical attention if they experience symptoms associated with risks of serious infections or meningococcal infections associated with ENJAYMO™ (sutimlimab)?
- Yes
 - No
 - I don't know/am not sure
20. Have you previously participated as an investigator of a clinical trial assessing ENJAYMO™ (sutimlimab) treatment?
- Yes
 - No
 - Prefer not to answer
21. Are you involved in the CADENCE patient registry for Cold Agglutinin Disease and Cold Agglutinin Syndrome?
- Yes
 - No
 - Prefer not to answer

CLOSING

Thank you for taking the time to complete this survey.

You may now close this browser.

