9.4 Study Population

Generally, it is preferable to conduct surveys to assess HCPs' knowledge and awareness of product-specific aRMM amongst HCPs actually engaging with the product (e.g., prescribers or HCPs managing care for patients receiving the product). However, since ENJAYMO™ is used to treat CAD, a rare disease, and will also be a newly authorised product where reimbursement applications and decisions will be ongoing, the number of prescribers may be low and therefore it may be challenging to identify a sufficient number of HCP prescribers to obtain robust and precise estimates of knowledge level. This survey will therefore be open to any HCP who was targeted to receive the aRMM for the product and is likely to prescribe (even though may not have yet prescribed) ENJAYMO™.

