9.4.2 Inclusion Criteria

HCPs will be eligible for this survey if they meet the following criteria:

1. Prescribers, and potential prescribers, of ENJAYMO™.
2. Provides permission to share their responses in aggregate with EMA or national competent authorities, if requested.

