9.7 Study Size

A sample of 50 completed surveys is targeted for this study, with possibly 10 of the HCPs having actually prescribed ENJAYMO™ (this number depends on uptake of ENJAYMO™ and is very difficult to predict). Although reasonable efforts will be made to reach the target, the actual sample size will depend on actual prescribing of ENJAYMO™ as well as HCPs' willingness to participate. The sample size was determined based on both feasibility and statistical considerations, giving the rarity of CAD and therefore anticipated low number of actual ENJAYMO™ prescribers.

A recent meta-analysis of data from 23 HCP surveys found the proportions of HCPs who completed a survey among those invited ranged from 0.5% to 26.0%, with a pooled estimated proportion of 2.1% (95% confidence interval [CI]: 2.1-2.2) based on a fixed effects model, or 4.7% (95% CI: 3.0-6.6) based on a random effects model(4). Based on this plus the ICON's anecdotal experience with similar surveys, this survey estimates that a response rate of 5% is achievable. Based on this estimated response rate, at least 1,000 HCPs may need to be contacted to obtain 50 completed surveys.

Error! Reference source not found. below provides the precision and 2-sided 95% CI for different assumptions regarding levels of knowledge and number of completed surveys for this study. The primary evaluation criteria is the composite weighted average knowledge levels for the core question set. With a response from 50 HCPs and an observed knowledge level of 80%, the true value would be estimated to lie within the margin of 68.9-91.1% (i.e. with a precision of 11.1%).

Table 9-3: Precision and 95% Confidence Intervals for Various Combinations of Sample Size and Knowledge Levels

Sample Size	Probable Respondent Knowledge Levels							
	60%		70%		80%		90%	
	Precision (%)	95% CI	Precision (%)	95% CI	Precision (%)	95% CI	Precision (%)	95% CI
25	19.2	40.8, 79.2	18.0	52.0, 88.0	15.7	64.3, 95.7	10.9	78.2, 100.0
50	13.6	46.4, 73.6	12.7	57.3, 82.7	11.1	68.9, 91.1	8.3	81.7, 98.3
75	11.1	48.9, 71.1	10.4	59.6, 80.4	9.1	70.9, 89.1	6.8	83.2, 96.8
100	9.6	50.4, 69.6	9.0	61.0, 79.0	7.8	72.2, 87.8	5.9	84.1, 95.9

Note: Calculated using PASS 12 software,* confidence intervals for 1 proportion, simple asymptotic formula.

* Hintze, J. (2014). PASS 12. NCSS, LLC. Kaysville, Utah, USA. www.ncss.com.

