9.11 Limitations of the Research Methods

A primary limitation of this cross-sectional survey is potential selection bias due to use of a convenience sample and/or low response rates. Moreover, the rarity of CAD and the relatively recent approval (meaning reimbursement in many EU countries may not yet or may only recently be available) may compromise the ability to identify a sufficiently large number of ENJAYMO™ prescribers to complete the survey. Therefore, the survey will be conducted amongst HCPs who treat CAD and were sent the ENJAYMO™ Physician's Guide, rather than limiting the survey to only ENJAYMO™ prescribers. Analyses will be performed stratified by ENJAYMO™ prescribing status.

The impact of selection bias can be minimized through robust outreach to recruit a representative sample of HCPs who have received the ENJAYMO™ Physician's Guide. For this survey, to minimize selection bias, HCPs from a broadly representative sample of European countries, geographically and via market-share, will be invited to participate. Countries in the EEA where the product is expected to be commercially available for at least 6 months may be included.

Generalizability of the study results may be limited in that the study population is based on a convenience sample. To improve generalizability, all HCP potential prescribers from included countries who were sent the ENJAYMO™ Physician's Guide, will be invited to participate in the survey (where sharing HCP contact information is allowed/available). To further endeavor to minimize selection bias:

- HCPs who have not responded will receive up to two reminders to encourage their participation.
- The HCP eligibility criteria are limited to target a broad population of HCPs available to prescribe ENJAYMO™.
- Where appropriate, HCPs will be offered a small reimbursement, based on FMV, for their time to complete the survey.

- Where HCPs are not able to commit to completing the survey, they will be provided the option to respond to one question indicating their reason for not participating in the survey.

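### The survey introduction describes the audience as prescribers only, although the protocol deliberately admits potential prescribers and expects them to be most of the sample

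*Protocol*

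**What the plan says.** In Annex 3, after the country page and before the screening questions, the Survey Introduction states that "ICON is conducting a survey among healthcare professionals who prescribe ENJAYMO™". It adds that eligibility criteria must be met, does not list them, and asks the reader to click on to find out whether they qualify.

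The body of the protocol defines a wider population:

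- Section 9.4.2, criterion 1 (repeated in the Synopsis): "Prescribers, and potential prescribers, of ENJAYMO™".
- Section 9.4 opens the survey to any clinician who was a target for the risk minimisation material and "is likely to prescribe (even though may not have yet prescribed) ENJAYMO™". The reason given is that actual prescribers may be too few in a rare disease with a new product.
- Section 9.11 says the survey covers clinicians who treat the disease and were sent the Guide, "rather than limiting the survey to only ENJAYMO™ prescribers".
- Section 9.7: "A sample of 50 completed surveys is targeted for this study, with possibly 10 of the HCPs having actually prescribed ENJAYMO™", with the number of prescribers described as very difficult to predict.

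**The concern.** The only statement in the introduction about who is wanted leaves out the group expected to supply most of the responses. A clinician who was sent the Guide but has never prescribed could reasonably take the sentence to mean that the survey is for others, and could leave before reaching question S1. Anyone who leaves there cannot be recovered by the screener.

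Two things are at stake. The first is the number of completes: the 80% assessment applies only when at least 30 have answered, and fewer than 30 completes triggers a second wave. The second is composition: Section 9.9.1.2 lists prescribing status among the factors that could confound the knowledge level, so a changed mix could move the pooled composite. Section 9.11 names selection bias as a primary limitation and lists steps against it, and this sentence works against those steps.

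**Working it through.** **Reproducing the plan's figures (Section 9.7).**
- Invitations needed: 50 / 0.05 = 1,000, as stated. Section 9.1.1 allows up to 1,000, so the number needed equals that ceiling.
- Half-width at n = 50 and 80% knowledge: 1.96 × √(0.80 × 0.20 / 50) = 11.1 points, giving 68.9% to 91.1%, as stated.
- Potential prescribers implied by the planning figure: 50 − 10 = 40, or 80% of the sample.

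**Following a non-prescriber through the questionnaire.** The introduction describes the audience as prescribers. S1 asks only whether the practice includes patients with the disease, S2 asks for permission to share responses, and S3 asks about employment. None asks about prescribing. Question 11 offers a response for having treated no patients and routes it onward. The instrument therefore accepts non-prescribers at every step, and only the introductory sentence conflicts with the design.

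**Illustration of loss.** The protocol gives no drop-out rate at the introduction. Let d be the assumed fraction of the 40 potential prescribers who leave and are not replaced. Then n = 10 + 40(1 − d), the prescriber share is 10/n, and the half-width at 80% is 1.96 × √(0.16/n).

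| d (assumed) | Completes n | Prescriber share | Half-width at 80% |
|---|---|---|---|
| 0 (plan) | 50 | 20% | 11.1 points |
| 10% | 46 | 22% | 11.6 points |
| 25% | 40 | 25% | 12.4 points |
| 50% | 30 | 33% | 14.3 points |
| 75% | 20 | 50% | 17.5 points |

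**Effect on the pooled level.** The shift equals (new prescriber share − 0.20) × (knowledge in prescribers − knowledge in potential prescribers). The protocol gives neither knowledge level, so both the sign and the size of the second factor are unknown. Results under assumed pairs:

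- 90% and 75%: 78.0% as planned, then 78.3%, 78.8%, 80.0% and 82.5% at losses of 10%, 25%, 50% and 75%.
- 85% and 78%: 79.4% as planned, 80.3% at 50% loss.
- 95% and 70%: 75.0% as planned, 78.3% at 50% loss, still below 80%.
- If prescribers knew less than potential prescribers, the shift would be downward.

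Whether the 80% line is crossed depends entirely on the values assumed.

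**What the planned analysis would do.** Sections 9.9.1.2 and 9.11 stratify by prescribing status, so a changed mix would be visible. The composite in Section 9.9.1.2 is weighted by item denominators and not standardised to a prescriber mix, so the pooled figure would not be corrected.

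**The case against.** The strongest reply is that the text excludes nobody. It ends by sending the reader to check eligibility, the screener admits non-prescribers and tells those who pass that they qualify, and question 11 has a path for them. The introduction is also not the first contact: Section 9.1.1 describes an individual invitation with information about the survey. That letter (Annex 2) was not in the text available, and it may already make clear that potential prescribers are wanted.

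The protocol also has ways to recover numbers: up to two reminders, encouragement by medical liaisons, wider outreach, more countries, a longer survey period and a second wave. Clinicians who cannot commit may give a reason, which could reveal a belief that they are ineligible. Even 30 completes would meet the floor.

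Finally, no target mix is fixed. Section 9.4 says that surveying those who use the product is generally preferable, so a higher prescriber share is not clearly a departure from a target.

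Most of this stands. A reader might infer that potential prescribers are being told to leave, that the sample will be enriched for prescribers, or that the composite will be biased upward past 80%. The documents support none of these. The reply does not remove the contradiction itself. Reminders and a second wave would lead to the same sentence, since the second wave uses the same survey, and the screener reaches only those who continue.

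**Conclusion.** The contradiction is certain: text shown to every respondent who reaches the introduction disagrees with inclusion criterion 1 and with Sections 9.4 and 9.11. It concerns about 40 of 50 expected respondents, a figure that rests on the protocol's own uncertain estimate of possibly 10 prescribers.

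The consequence is possible, not demonstrated. Some potential prescribers may be discouraged, which would lower the number of completes and raise the prescriber share. The range of 46 to 20 completes and 22% to 50% prescribers assumes losses of 10% to 75% with no replacement, and the protocol does provide for replacement. A claim that the wording turns a missed criterion into a met one would need a loss rate and two knowledge levels that the documents do not give, so the direction and size of any effect on the 80% assessment remain undetermined.

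The point is still worth correcting. The sentence is part of the instrument, no later analysis brings back people who left, and the pooled composite is not adjusted for prescriber mix.

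**What to change.** Reword the opening of the Annex 3 introduction so that it describes the survey as being among *healthcare professionals who treat cold agglutinin disease and who prescribe, or may in future prescribe, ENJAYMO; you do not need to have prescribed it to take part*. Translate the sentence into German, Italian and Dutch, and check that the invitation letter in Annex 2 describes the same audience.

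The cost is one sentence, its translations and their review. No planned figure changes: the target stays at 50 completes, the planning mix at 10 and 40, and the half-width at 11.1 points. There is no real downside.
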